#### 9.4.1. General considerations

#### 9.4.2. Primary endpoint(s)

Medication usage; total amount of propofol used (mg/kg/hr) from start to end of anesthesia.

TCI effect site target at start, and each 10 min interval during anesthesia.

#### **9.4.3. Secondary endpoint(s)**

Time to wake-up; from halt of anesthetic drugs to

- extubation (sec)
- Verbal respons (sec)
- Motoric response (show right index finger)(sec)

Medication usage of remifentanil micg/kg/min

Medication usage of inotropes (phenylephrine, norepinephrine)

Cognitive function, assessed with 4 trials in the CANTAB IPAD-tool, preoperative function compared with 3hrs after wake-up, and preoperative compared with 24 hrs after wake-up.

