### Objectives and Endpoints

Objectives	Endpoints
Primary	

 
Use of DoA-mon reduces anesthetic dosage and wake-up times
 
	
 
Total amount of propofol (mg/kg/hr) administered
 
Time to wake-up after halt of anesthetic administration
 

Secondary	

 
Use of DoA-mon reduces POCD
 
	
 
Cognitive functioning
 

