### 3. Objectives and Endpoints

Objectives	Endpoints
Primary	

• Use of DoA-mon reduces anesthetic dosage and wake-up times

	

• Total amount of propofol (mg/kg/hr) administered

• Time to wake-up after stop of anesthetic administration

Secondary	

• Use of DoA-mon reduces POCD

	

• Cognitive functioning

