## 9. Statistical Considerations

### 9.1. Statistical Hypotheses

We anticipate that wake-up happens at mean 15 min, standard deviation 5 min (41-44) in the control group. We hypothesize that there will be an improvement of 20% (3 min) in the intervention group.

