### 9.2. Sample Size Determination

We hypothesize that the intervention will reduce amount of propofol administered by up to 20%, also that wake-up may be reduced from 15 min, SD 5 min – to 20 min SD 3 min. With an improvement of 20%, 80% power and a significance level of 0.05, the study will require 88 patients in total, calculated in a two-sample t-test. To add for margin of error/loss we will include 50 patients in each group, summing at 100 patients in total. Due to a difference in plasma levels of anesthetic drugs in men and women, we will do gender stratification when randomizing, to ensure an equal number of sexes in both groups.

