### 9.4. Statistical Analyses

The statistical analysis plan will be finalized prior to database lock, and it will include a more technical and detailed description of the statistical analyses described in this section. This section is a summary of the planned statistical analyses of the most important endpoints including primary and key secondary endpoints.

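### Time to wake-up is primary in Sections 1.1 and 3 but secondary in 9.4.3, yet the stated 80% power belongs to it; propofol, the only endpoint primary in every list, has no power calculation

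*Protocol*

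**What the plan says.** The primary endpoints are listed in three places in the protocol.

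- The Section 1.1 synopsis lists propofol (mg/kg/hr) and "Time to wake-up after halt of anesthetic administration".
- Section 3 lists the same pair, the second as "Time to wake-up after stop of anesthetic administration".
- Section 9.4.2 keeps propofol but pairs it with "TCI effect site target at start, and each 10 min interval during anesthesia". Wake-up is not there.

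Section 9.4.3 then has wake-up as a secondary endpoint, "Time to wake-up; from halt of anesthetic drugs to" each of three events: extubation, verbal response and a motor response.

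On sample size, Section 9.1 gives one hypothesis, for wake-up: "We anticipate that wake-up happens at mean 15 min, standard deviation 5 min" in the control group, with a 20% (3 min) improvement. Section 9.2 says "With an improvement of 20%, 80% power and a significance level of 0.05, the study will require 88 patients in total", using a two-sample t-test, and raises this to 100. For propofol it says only "We hypothesize that the intervention will reduce amount of propofol administered by up to 20"%. Section 9.4 adds that "The statistical analysis plan will be finalized prior to database lock".

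**The concern.** The endpoint lists conflict within the current text, and the sample size is tied to the endpoint whose status is in dispute. If Section 9.4 governs, the 80% power was computed for a secondary endpoint and the primary endpoints have none. If Section 3 governs, one of two primary endpoints has a calculation and the other does not. A single significance level of 0.05 is given, with no indication of which endpoint it applies to or whether one or both must succeed.

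Suppose wake-up improves and propofol use does not. The trial might be reported as positive under Section 3 and negative under Section 9.4. The split into three wake-up events adds a further choice, because Section 9.1 does not say which event the 15 min (SD 5) describes.

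**Working it through.** **1. The lists side by side**

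| Endpoint | Sections 1.1 and 3 | Section 9.4 | Mean and SD given? |
|---|---|---|---|
| Propofol, mg/kg/hr | primary | primary (9.4.2) | no |
| Time to wake-up | primary | secondary, three events (9.4.3) | yes (9.1) |
| TCI effect-site target | not listed | primary (9.4.2) | no |

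Only propofol is primary throughout.

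**2. Reproducing the 88**

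Inputs from Sections 9.1 and 9.2: difference 3 min, SD 5 min, 80% power, significance level 0.05. Sidedness is not stated; two-sided is assumed because it reproduces the figure.

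n per arm = 2 × [SD × (1.960 + 0.842) / difference]² = 2 × (5 × 2.802 / 3)² = 43.6, so 44 per arm and 88 in total.

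With the exact noncentral t distribution the requirement is 44.6 per arm (90 in total). Power is 79.5% at 44 per arm and 84.4% at 50 per arm. The stated figure is therefore reproduced.

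Three alternatives do not give 88:
- One-sided 0.05 with the same inputs gives 70.
- The values printed in Section 9.2 (15 min SD 5 to 20 min SD 3) need 12 per arm, 24 in total, by the t-test.
- A 3 min difference with SDs 5 and 3 needs 62 in total.

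**3. What the 88 would mean for propofol**

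No mean or SD is given, so the CV (SD divided by the control mean) is an assumption. The standardised difference for a 20% reduction is 0.20 / CV. The wake-up inputs are themselves a 20% change (3/15) at a CV of 33% (5/15), so 88 carries over to propofol only if its CV is about the same. Two-sided t-test at 0.05:

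| Assumed CV | Power at 50 per arm | Total N for 80% |
|---|---|---|
| 25% | 98% | 52 |
| 30% | 91% | 74 |
| 33% | 85% | 88 |
| 40% | 70% | 128 |
| 50% | 51% | 200 |

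The largest CV giving 80% power is 0.331 at 44 per arm and 0.353 at 50 per arm. The stated reduction is also an upper bound: a 15% reduction at CV 33% has 61% power at 50 per arm.

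**4. Why the decision rule matters (illustration only, since none is stated)**

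- If either endpoint suffices at 0.05 each, the false-positive rate is at most 1 − 0.95² = 9.75% for independent endpoints, falling to 8.3% at correlation 0.7.
- If both are required at 50 per arm, joint power at correlation 0 is 0.844 × 0.851 = 71.8% at CV 33% and 0.844 × 0.697 = 58.8% at CV 40%. At correlation 0.7 these become 77.5% and 66.0%.

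**The case against.** The best defence is that Section 9.4.3 is simply the outlier. Wake-up is primary in both objectives tables and is the only endpoint with a full hypothesis. On that reading the 80% power does belong to a declared primary endpoint, and the TCI line may be only a dosing profile. This is plausible, and it may be what the sponsor meant. But the text does not say so, and Section 9.4 is the part that the analysis plan is to elaborate. Even on this reading, propofol is primary without a power calculation.

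It can also be said that testing order and multiplicity belong in the analysis plan. That is fair for the details, and the error-rate and joint-power figures above are illustrations that do not carry the conclusion. Which endpoints are primary, however, is something the protocol itself states, and states in two ways. An analysis plan that follows either version contradicts the other.

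Two further points stand. First, nothing here shows that propofol is underpowered; at a CV of 25% it has ample power. Second, the 20% improvement in Section 9.2 follows a sentence naming both endpoints, and a propofol CV of 33% would also give 88. The accurate statement is that wake-up is the only endpoint with stated inputs that lead to 88.

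**Conclusion.** The point holds. The primary lists in Sections 1.1 and 3 and in Section 9.4 are incompatible. The stated 80% power (84% at 50 per arm) is for time to wake-up, assuming a two-sided test, and it does not cover propofol. Propofol power at 50 per arm runs from 98% to 51% over assumed CVs of 25% to 50%, and reaches 80% only if the CV is about 35% or less and the true reduction is the full 20%. The contradiction and the 88 rest on the protocol alone; the propofol figures rest on the assumed CV. Because this concerns which result decides the trial, it must be settled before any comparison by arm.

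**What to change.** 1. Use one identical primary list in Sections 1.1, 3 and 9.4.
2. Name a single wake-up event. Section 9.1 does not identify the one its 15 min (SD 5) describes, so the sponsor must establish that from the sources cited there. The wake-up power stays valid only for that event.
3. Move the TCI profile and the other two wake-up times to secondary or descriptive status.
4. State the decision rule. One example that keeps the present sample size is a fixed sequence at two-sided 0.05: first the named wake-up event, then propofol only if the first succeeds. Propofol first, or both required, is equally open to the sponsor, with the power restated to match.
5. In every case state the assumed propofol CV and a definite reduction to be detected, not an upper bound.

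The cost is a protocol amendment with IRB/IEC approval (Section 10.1.1), before database lock and before any comparison by arm. No new data are needed if wake-up leads. The price of that sequence is that propofol cannot be claimed if wake-up fails: the chance of claiming both is about 72–77% at CV 33% and 59–66% at CV 40%, for correlations from 0 to 0.7. If propofol leads and its CV is above about 35%, 100 patients no longer give 80% power (128 are needed at CV 40%). The sponsor would then have to enlarge the trial or state the lower power.

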## 4. Study Design

This is a randomized controlled blinded study, with two groups; intervention and control.

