### 4.1. Overall Design

Both groups will receive standard of care in total intravenous anesthesia (TIVA), with monitoring of clinical signs relating to level of anesthesia and to the satisfaction of the surgeon. In the intervention group, the anesthesia providers will guide the dosage of hypnotics based on a BIS-index of 45-60 perioperative, also avoiding burst-suppression (visually detected)/suppression-ratio (SR) of 0, and EEG-frequency alpha (peak alpha) of 10-12 hz.

All patients will have a recording of their perioperative EEG. All patients will be assessed pre and postoperatively using the Cambridge Neuropsychological Automated Test Battery (CANTAB) to assess how they are affected, testing for executive cognitive functioning. The participants use an IPAD to self-assess, so the assessor is blinded.

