#### Medical Conditions

4. Psychiatric disorders
5. Pregnancy
6. Breast feeding
7. Using antiepileptic drugs.
8. Central neurological disease
9. Unable to complete baseline CANTAB-test.

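### Section 9.4.3 frames cognition as change from the preoperative score; a between-arm difference adjusted for that score and for sex would be more precise at almost no cost, and the assessment clock should be the same throughout.

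*Protocol*

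**What the plan says.** - **Objective (section 3).** The secondary objective is comparative: "Use of DoA-mon reduces POCD". Its endpoint is cognitive functioning.
- **Design (section 4).** "This is a randomized controlled blinded study, with two groups; intervention and control".
- **Analysis (section 9.4.3).** Cognition is measured with four CANTAB trials, and the comparison is written as "preoperative function compared with 3hrs after wake-up, and preoperative compared with 24 hrs after wake-up". Section 4.1 gives the same pre/post picture: "All patients will be assessed pre and postoperatively using the Cambridge Neuropsychological Automated Test Battery (CANTAB) to assess how they are affected".
- **Status of section 9.4.** "This section is a summary of the planned statistical analyses of the most important endpoints including primary and key secondary endpoints". A more technical description is left to the SAP.
- **Available covariates.** One exclusion criterion in section 5.2 is "Unable to complete baseline CANTAB-test", so every eligible patient has a preoperative score. Section 9.2 adds that "we will do gender stratification when randomizing, to ensure an equal number of sexes in both groups".
- **Time origin.** The synopsis and the Schedule of Activities place the two postoperative assessments at 3 h and 24 h after surgery. Section 9.4.3 counts the same hours from wake-up.

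**The concern.** The cognition line names two time points in the same patient and no arm. The sensible reading is a change score whose arm contrast follows from the randomised design. On that reading, the estimate subtracts the whole preoperative score from the postoperative one, whatever the correlation between them. When that correlation is moderate, the subtraction carries noise from the preoperative measurement into the outcome. Regressing on the preoperative score removes only the part that predicts the outcome.

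What is at stake is the precision of a secondary endpoint in a trial sized for wake-up time. The sample size and the primary endpoints are not affected.

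The second, smaller matter is that the same visits are timed from two different moments. One of these, wake-up, is itself an outcome that the intervention is expected to shift, and 9.4.3 records it at three events (extubation, verbal response, motor response).

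**Working it through.** **The plan's own figure.** Sections 9.1 and 9.2 give, for wake-up, a 3 min difference, SD 5 min, 80% power and significance level 0.05 (two-sided assumed). By the normal approximation, n per arm = 2 × (1.960 + 0.842)² × 5² / 3² = 43.6, so 44 per arm and 88 in total. This agrees with "the study will require 88 patients in total, calculated in a two-sample t-test". (The exact t calculation gives 44.6 per arm, so 45.) The protocol gives no such calculation for cognition. Its planned 50 per arm is therefore taken as fixed, and 44 per arm is shown as well.

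**Assumptions.** The protocol gives no CANTAB SD and no pre/post correlation. I take r = 0.3, 0.5, 0.7, and k = preoperative SD / postoperative SD = 0.8, 1, 1.25. Differences are in postoperative SD units.

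**Variance per patient.**
- Change score: k² + 1 − 2rk = (1 − r²) + (k − r)²
- Adjusted for preoperative score: 1 − r²
- Ratio, adjusted over change: (1 − r²) / [(1 − r²) + (k − r)²]. This cannot exceed 1, and at k = 1 it equals (1 + r)/2.

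The reduction in detectable difference is 1 − √ratio.

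| k | r = 0.3 | r = 0.5 | r = 0.7 |
|---|---|---|---|
| 0.8 | ratio 0.784, 11% smaller | 0.893, 5.5% | 0.981, 1% |
| 1 | 0.650, 19% | 0.750, 13% | 0.850, 8% |
| 1.25 | 0.502, 29% | 0.571, 24% | 0.628, 21% |

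Worked example, k = 1.25 and r = 0.5: 0.75 / (0.75 + 0.75²) = 0.75 / 1.3125 = 0.571, and 1 − √0.571 = 0.24.

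A simulation of 20,000 trials with 50 per arm, k = 1, and a model with arm, sex and preoperative score gave ratios of 0.651, 0.756 and 0.853. The cost of the extra degrees of freedom is therefore negligible.

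**Detectable difference at 80% power, two-sided 0.05, k = 1 (noncentral t).** With 50 per arm, a two-sample comparison detects 0.566 SD. Multiply by √(2(1 − r)) for change and by √(1 − r²) for the adjusted analysis.

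| | r = 0.3 | r = 0.5 | r = 0.7 |
|---|---|---|---|
| 50 per arm, change | 0.670 | 0.566 | 0.438 |
| 50 per arm, adjusted | 0.540 | 0.490 | 0.404 |
| 44 per arm, change | 0.715 | 0.604 | 0.468 |
| 44 per arm, adjusted | 0.576 | 0.523 | 0.431 |

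For an assumed true arm difference of 0.5 SD with 50 per arm, power is 55%, 70% and 89% with change scores, against 74%, 82% and 93% adjusted.

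**Clock.** The anticipated arm difference in wake-up is 3 min, and 3/180 = 1.7% of 3 h. If end of surgery and wake-up lie 15 min apart (an assumption, because 9.4.3 times wake-up from the halt of anaesthetic drugs), the two origins differ by 15/180 = 8.3% of 3 h and 15/1440 = 1.0% of 24 h.

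**The case against.** **The model belongs in the SAP.** The choice between change and adjusted analysis is ordinary SAP content, and its absence from a protocol is not an error. This stands, and the point is therefore made as an improvement and not as an omission. It is still worth writing in 9.4.3, because that section already words the comparison as pre versus post and the SAP is meant to elaborate it.

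**A reader might infer that the plan is to test pre versus post within each arm.** Such tests would not address the objective. If both arms truly changed by the same 0.1 to 0.3 SD, with r of 0.5 to 0.7 and 50 per arm, exactly one arm would be significant with probability 0.19 to 0.49. The protocol does not support this inference. Sections 9.4.2 to 9.4.4 write an arm contrast for no endpoint; they list what is measured. In that list the cognition line defines the measure, and the contrast comes from the objective and the two-arm design. Nowhere are separate within-arm tests planned. Nor is it fair to say that the plan leaves unclear what would count as evidence.

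**A reader might also see a contradiction in the baseline date,** since the synopsis mentions assessment one day before surgery and the Schedule of Activities marks preoperative CANTAB only at screening, up to 14 days before. It is not one. The synopsis sentence does not name CANTAB, and the Day -1 column carries other assessments (vital signs, height and weight, pain and sedation).

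**The size rests on assumed values.** This also stands. The power contrast of 55% against 74% is the favourable low-correlation case; at r = 0.7 it is 89% against 93%. Only the direction is independent of the assumptions.

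**Conclusion.** The comparison as most naturally read, change from baseline between randomised arms, is valid. It is less precise than it could be with data the trial already collects. With 50 per arm, adjustment makes the detectable difference 19%, 13% or 8% smaller at r = 0.3, 0.5, 0.7 and equal SDs, and about 1% to 29% smaller over SD ratios of 0.8 to 1.25. It is never a loss beyond negligible degrees of freedom. These sizes rest on assumed correlations, assumed SD ratios and a roughly linear pre/post relation. The endpoint is secondary and the sample size does not change. Adjustment is the better choice, not the only correct one.

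The mismatch in time origin is a real inconsistency of small size and needs only wording.

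**What to change.** In section 9.4.3, state that the effect is the between-arm difference in CANTAB score at 3 h and at 24 h, each estimated from a linear model with arm, preoperative score on the same test, and sex (the randomisation stratum).

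Use one time origin for these assessments in the synopsis, the Schedule of Activities and 9.4.3. End of surgery is preferable: two of the three places already count from surgery, and wake-up is itself an outcome recorded at three events.

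Lead measure, multiplicity across the four tests and two time points, any transformation and any POCD threshold can stay with the SAP.

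The cost is one sentence and a wording alignment, with no extra tests, visits or patients. A skewed CANTAB measure may need a transformation for the linear model. The gain will be small if the correlation is high and postoperative scores are more spread than preoperative ones.

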#### **9.4.4. Other safety Analyse(s)**

Adverse events

## **10. Supporting Documentation and Operational Considerations**

### **10.1. Appendix 1: Regulatory, Ethical, and Study Oversight Considerations**

#### **10.1.1. Regulatory and Ethical Considerations**

- This study will be conducted in accordance with the protocol and with the following:
  - Consensus ethical principles derived from international guidelines including the Declaration of Helsinki and Council for International Organizations of Medical Sciences (CIOMS) International Ethical Guidelines
  - Applicable ICH Good Clinical Practice (GCP) Guidelines
  - Applicable laws and regulations
- The protocol, protocol amendments, ICF, Investigator Brochure, and other relevant documents (e.g., advertisements) must be submitted to an IRB/IEC by the investigator and reviewed and approved by the IRB/IEC before the study is initiated.
- Any amendments to the protocol will require IRB/IEC approval before implementation of changes made to the study design, except for changes necessary to eliminate an immediate hazard to study participants.
- The investigator will be responsible for the following:
  - Providing written summaries of the status of the study to the IRB/IEC annually or more frequently in accordance with the requirements, policies, and procedures established by the IRB/IEC
  - Notifying the IRB/IEC of SAEs or other significant safety findings as required by IRB/IEC procedures
  - Providing oversight of the conduct of the study at the site and adherence to requirements of 21 CFR, ICH guidelines, the IRB/IEC, European regulation 536/2014 for clinical studies (if applicable), and all other applicable local regulations

#### **10.1.2. Financial Disclosure**

This study is financed in total by the investigator/sponsors hospital; either through the investigators PhD-fellowship program, or equipment purchased by the anesthetic department of said hospital.

#### **10.1.3. Informed Consent Process**

- The investigator or his/her representative will explain the nature of the study to the participant or his/her legally authorized representative and answer all questions regarding the study.
- Participants must be informed that their participation is voluntary. Participants will be required to sign a statement of informed consent that meets the requirements of 21 CFR

50, local regulations, ICH guidelines, Health Insurance Portability and Accountability Act (HIPAA) requirements, where applicable, and the IRB/IEC or study center.

- The medical record must include a statement that written informed consent was obtained before the participant was enrolled in the study and the date the written consent was obtained. The authorized person obtaining the informed consent must also sign the ICF.
- Participants must be re-consented to the most current version of the ICF(s) during their participation in the study.
- A copy of the ICF(s) must be provided to the participant or the participant's legally authorized representative.

#### **10.1.4. Data Protection**

- Participants will be assigned a unique identifier by the sponsor.
- The participant must be informed that his/her personal study-related data will be used by the sponsor in accordance with local data protection law. The level of disclosure must also be explained to the participant who will be required to give consent for their data to be used as described in the informed consent
- Third party software providers (Cambridge Cognition), will store data from the CANTAB cognitive assessment tests as without name or information which would make the participant identifiable. These results will be stored on extra safe servers belonging to Cambridge Cognition in the UK, accessed only by principal investigator and PhD-fellow in the study-group. The handling of this data is covered in the DAP agreement between sponsor, and Cambridge Cognition.

